50	Appendix A – Study Schedule	
Table A.1 - Schedule of Study Procedures
 
  
 Evaluation	Visits*	
 
 Screening (enrollment)	Study Procedure	
   
 Written Informed Consent	X		
 
 Patient Demographics	X		
 
 Inclusion criteria	X		
 
 Exclusion criteria	X		
 
 Blood draw		X	
  
 
*Subjects will be followed for AE reporting purposes from the time the parent(s) or LAR/LDR(s) provided written consent to end of study procedures. There will be no follow-up after the completion of the study.
	Evaluation	Visits*		Screening (enrollment)	Study Procedure	Written Informed Consent	X		Patient Demographics	X		Inclusion criteria	X		Exclusion criteria	X		Blood draw		X	Administrative change. The change made does not impact the study design or risk.
Evaluation	Visits*																						
	Screening (enrollment)	Study Procedure																					
Written Informed Consent	X																						
Patient Demographics	X																						
Inclusion criteria	X																						
Exclusion criteria	X																						
Blood draw		X																					

Study Title: U-TruSignal SpO2 Testing in Neonates

Study No: 123.04-2017-GES-0002

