3.3 Summary of Study Design

This is a pre-market, clinical, open label, prospective, non-randomized research study conducted at 2 sites.

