5.3 Description of Study Procedures

The following are the steps to be performed:

- 1) To document the case, photographs of the position of the measurement sensors and other equipment may be taken at the request of the Sponsor at any point of the procedure, when necessary.
Note: photographs are taken in a way that the subject cannot be identified from the pictures.
- 2) Apply sensor(s) to the subject as appropriate. No more than one SpO₂ sensor placed on the same limb, and no sensor placed close to blood draw site/IV cannulation (same limb). Record site of sensor(s) placed on the CRF.
- 3) Allow the clinical environment and readings to stabilize.
- 4) Start data collection using the data collection tool.
- 5) Collect data using the data collection tool for a minimum of 10 minutes prior to routine arterial blood draw, per the data collection tool. Record possible accidental annotations in CRF.
Note: The arterial blood draw collected during this study will be performed according to the site's standard of care and will not be prescribed by the Sponsor.
- 6) When routine arterial blood draw is conducted, mark arterial blood draw time with data collection tool. The blood sample will be processed through hospital's standard procedure. Record possible accidental annotations in CRF.
- 7) After arterial blood draw, continue collecting data using the data collection tool for a minimum of 2 minutes. Record possible accidental annotations in CRF. Stop data collection.
- 8) Remove sensor(s) from the subject.
- 9) Monitor and record the following information using the data collection tool or recording on CRF during steps 4-7):
 - a. clinical status notes; i.e., frequent apnea, hemodynamic instability, abnormal heart rhythm, or other status;
 - b. environmental conditions such as changes in lightning conditions, ongoing care moving the neonate outside blood sampling, excessive clinical signs such as agitation, readjustment of a sensor; AND
 - c. notes regarding data collection such as accidental annotations.
- 10) Obtain results of the arterial blood draw and record possible errors during standard procedure for blood sampling and analysis.
- 11) Repeat Steps 1-10 up to 3 times to obtain a maximum of 6 data pairs, 3 data pairs per sensor aiming to collect equal data for each sensor.

Note: Alternate the sensors used; e.g., if TS-AF was used first, then TS-SE should be used at the next data collection.

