6. STUDY DATA COLLECTION AND ASSESSMENTS

6.1 Primary Assessment

The Investigator or designated study staff will perform the collection of SpO₂ and pulse rate, that will be recorded in the U-TruSignal Data Collector. Laboratory results from arterial blood draw will be collected from the hospital's medical records.

The following data will be collected on the CRF:

- 1) Demographics: date of birth, gender, length, and weight, skin tone (see Appendix C – Modified Fitzpatrick Scale);
- 2) U-TruSignal Serial Number, Sensor Type, LOT Number, and Attachment Location of the Sensor;
- 3) Notes regarding data collection e.g. incorrect annotation of data file or several data files;
- 4) Relevant information on the clinical status affecting hemodynamic stability such as frequent apnea, hemodynamic instability, abnormal heart rhythm;
- 5) Environmental conditions e.g. open bed, changing lightning conditions, ongoing care causing movements, readjustment of a sensor.

The laboratory results will include and to be collected from the hospital's medical record:

- 1) Co-Oximeter information,
- 2) Functional SaO₂ (%),
- 3) Fractional oxyhemoglobin (FO₂Hb) [%],
- 4) Fractional carboxyhemoglobin (FCOHb) [%],
- 5) Fractional methemoglobin (MetHb) [FMetHb] [%],
- 6) Total hemoglobin (tHb) (ctHb) [g/L]
- 7) Fetal hemoglobin (Hb) [g/L] (calculated), and
- 8) Fractional fetal hemoglobin [%].

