44	Section 10.3.3 – Analysis of Primary Endpoint	Data analysis for the data collection interval, which is defined as the five (5) second period starting after a twelve (12) second technical delay from the time sampling occurs, will follow ISO80601-2-61, 2011, Annex EE and the FDA Guidance Document for Pulse Oximeters (FDA Guidance, March 4,	Administrative changes. The changes made do not impact the study design or risk.

		
2013). Separate analysis will be performed for each sensor type.
 
The ARMS accuracy Root Mean Square (ARMS) calculation is used as a means to define the SpO2 Accuracy. Arms will be calculated as
 $Arms = \sqrt{\frac{\sum_{i=1}^n (DUT_i - Ref_i)^2}{n}}$ 
, where
 
Ref_i = Reference CO-Oximeter Functional SaO2 of data pair i
 
DUT_i = Device Under Test SpO2 of data pair i
 
The difference between SpO2 and SaO2 will be summarized using mean, minimum and maximum. Number of subjects and number of data pairs will also be presented.
 
A least squares regression of SpO2 on SaO2 will be performed and results be presented with a regression plot and table.
 
Bland-Altman graphical plots, error (SpO2 – SaO2) versus average SaO2 will be generated with mean, and upper 95% and lower 95% limits of agreement according to Section 3 of “Agreement Between Methods Of Measurement With Multiple Observations Per Individual” by Bland and Altman in 2007 Journal of Biopharmaceutical Statistics. Individual test subjects will be color coded in the Bland-Altman graphical plot.
 
Data listed below will be excluded from analysis:
 
 ▪ Data with SaO2 < 70%, tHb < 10g/L, MetHb > 2%, COHb > 3%; ▪ Draws with values smaller than -0.5% in any of the Hb values; ▪ Artefacts/other external error sources indicated by clinical documentation or derived from the collected data around sampling including but not limited to: 
 ○ changes in sensor fit; ○ excessive movement during draw; ○ low perfusion (mod% < 0.5%); ○ irregular plethysmographic waveform or artefacts in the waveform; ▪ Data with error conditions on CO-Oximeter analysis indicated by clinical documentation e.g. air bubbles in syringe, clots, violation of hospital’s standard procedure; ▪ Data with error conditions on pulse oximeter; ▪ Unstable SpO2 readings from the respective device under test; 	
--	--	---	--

Study Title: U-TruSignal SpO2 Testing in Neonates

Study No: 123.04-2017-GES-0002

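### Reference-sample faults that remove a pair from the primary ARMS may be recorded once SaO2 is known, so exclusion can depend on the size of the error and ARMS can be biased low

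*Combined protocol and SAP*

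**What the plan says.** Section 10.3.3 (Analysis of Primary Endpoint) computes ARMS separately for each sensor type and lists data to be left out. One item is "Data with error conditions on CO-Oximeter analysis indicated by clinical documentation e.g. air bubbles in syringe, clots"; the examples go on to include violation of the hospital's standard procedure. The list is illustrative, not closed. Section 10.3.2 defines the analysis set as all valid data, so an excluded pair leaves the primary result. Section 10.3.3 promises a rationale for each exclusion. No ARMS with excluded pairs restored is planned.

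Section 5.3 says when things are written down. Step 9 reads "Monitor and record the following information using the data collection tool or recording on CRF during steps 4-7"; its items cover clinical status, environment and data-collection notes, and sample faults are not named. Step 10 reads "Obtain results of the arterial blood draw and record possible errors during standard procedure for blood sampling and analysis".

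On who knows what, section 3.3 states: "This is a pre-market, clinical, open label, prospective, non-randomized research study conducted at 2 sites". Section 5.3 step 3 is "Allow the clinical environment and readings to stabilize". Section 6.1 says "The Investigator or designated study staff will perform the collection of" SpO2 and pulse rate, and "Laboratory results from arterial blood draw will be collected from the" hospital's medical records. No section masks either value from the person who records faults.

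**The concern.** Whether a sample was faulty should be settled without knowing whether it agreed with the device. Here the recording of sampling and analysis faults is placed alongside receipt of SaO2, in a study with no masking. A draw that disagrees with the device invites a search for a bubble, a clot or a procedural lapse; a draw that agrees does not. Breach of procedure is also partly a matter of judgement.

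ARMS is a root mean square, so a few large differences dominate it. If those pairs are more likely to be dropped, the device looks more accurate than it is, and the minimum and maximum error and the limits of agreement narrow as well. Section 2.1 says the results are meant for regulatory submission in the United States and Europe.

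**Working it through.** **The plan's own counts.** Section 10.2 gives 50 to 70 pairs per sensor, up to 3 pairs per subject per sensor, 17 subjects at least and 140 at most. These fit together: 50 / 3 = 16.7, rounded up to 17 (17 × 3 = 51 pairs), and 70 subjects × 2 sensor types = 140. So n = 50 to 70 is the right range for one ARMS.

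**What the documents do not give.** There is no ARMS limit, error SD or expected exclusion rate, and section 10.1 says no hypothesis is tested. The effect is therefore expressed as a ratio, which needs no SD. The number of pairs lost, and how they are selected, are assumptions.

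**Formula.** With f the share of the sum of squared errors carried by the k lost pairs,

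ARMS after / ARMS before = √[ n/(n − k) × (1 − f) ].

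If exclusion ignores the error, f averages k/n and the ratio is about 1. If large errors are preferred, f exceeds k/n and the ratio falls below 1.

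**Simulation.** Independent normal errors with mean 0; 20,000 runs at n = 50 and 70, and 40,000 at n = 60. Mean ratio:

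| Pairs lost | 1 | 2 | 3 |
|---|---|---|---|
| Largest errors, n = 50 | 0.942 | 0.898 | 0.861 |
| Largest errors, n = 60 | 0.949 | 0.911 | 0.878 |
| Largest errors, n = 70 | 0.955 | 0.920 | 0.891 |
| Random from largest 20%, n = 50 | 0.977 | 0.953 | 0.927 |
| Random from largest 20%, n = 70 | 0.984 | 0.967 | 0.949 |
| Regardless of error, n = 50 or 70 | 1.000 | 1.000 | 1.000 |

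Reading one cell back through the formula: at n = 50 and k = 3, 1 − f ≈ 0.861² × 47/50 = 0.741 × 0.94 = 0.697. Six per cent of the pairs thus carry about 30% of the sum of squares.

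**Sensitivity to the error model.** A mean error of 0.5 SD at n = 50 gives 0.944, 0.902 and 0.865. With 17 subjects × 3 pairs and within-subject correlation 0.6, the ratios are 0.945, 0.903 and 0.867. Neither changes the picture.

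**A probabilistic case.** Assume true ARMS 3.3, n = 60, and a fault recorded for 25% of pairs off by more than 5 points but for 3% of the rest. Mean ARMS falls from 3.29 to 3.13 (3.13/3.29 = 0.951, about 5%). Excluding about the same share regardless of error leaves 3.28.

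**The other direction.** If 3 of 50 pairs carry genuine extra reference error with SD twice the device error SD, expected ARMS with them is about √[(47 × 1 + 3 × 5)/50] = √1.24 = 1.11 against a true value of 1. Removing them gives about 0.99. Excluding real faults corrects ARMS; only selective exclusion distorts it.

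**The case against.** The text leaves more room than a quick reading suggests.

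- A reader might infer that faults are recorded only after SaO2 is known. Section 10.3.3 is triggered by clinical documentation generally, not by a step 10 entry alone. The draw and analysis follow the hospital's procedure, which may already have logged the fault, and section 11.1.1 asks for CRF entry as information becomes available. Step 10 sets no order between seeing the result and noting a fault. This stands: earlier recording is permitted. It is not required.
- That staff see SpO2 is an inference from step 3 and section 6.1. The paired value comes from a 5-second window after a 12-second delay, and nothing says the fault recorder has it. This also stands, though sight of the readings is likely.
- A reader might infer that only the reference side is judged afterwards. Section 10.3.3 also excludes artefacts derived from the collected data, which can be judged only from the recording. The reference side is not unique in this.
- A reader might infer that the harm could not be undone. SpO2 stays in the electronic file with a copy at the site, SaO2 stays in the hospital record, and source documents are retained (sections 6.1, 11.1.1, 11.1.3). Where the analyser returned a value, a pair can be restored at any time. What may be lost is whether the fault was noted before or after the result.
- A rationale is required for every exclusion. That helps an auditor, but it does not show what the recorder knew when the fault was noted.

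**Conclusion.** The concern holds as a route to bias. Reference-side exclusions are open-ended, the only step that calls for recording them is the step that obtains SaO2, nothing fixes fault status beforehand, and no ARMS with these pairs restored is planned. It is tempting to conclude that ARMS is biased low. The documents do not support that: they show that it can happen, not that it will, and removing genuinely faulty samples is legitimate.

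If it did happen, the effect would matter at this sample size: about 5% to 14% for the 1 to 3 largest errors at 50 to 70 pairs, and about 2% to 7% for random loss from the largest 20% of 50. The first range is an upper case, since it assumes that the very largest errors are always the ones lost and that none reflects a real fault. With no stated ARMS limit, nothing follows about passing or failing. This is a worthwhile, inexpensive improvement to the plan; it does not invalidate the study.

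**What to change.** 1. In section 5.3, have study staff record visible sampling faults (air bubble, clot, procedure violation) on the CRF at step 6, with a time, before the SaO2 result is viewed. In step 10, transcribe the results, any analyser error flags and any fault reported by the hospital, and mark each fault as noted before or after the result was seen.
2. In section 10.3.3, list every pair excluded for a reference-side fault with its SpO2 − SaO2 difference (where a value exists) and its before/after mark. For each sensor, report ARMS with the planned exclusions and again with pairs restored whose fault was first noted after the result.

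The planned exclusions stay as they are, so a late-discovered clot need not count against the device in the primary figure. The hospital laboratory is given no new duty, in keeping with section 2.4.2. The cost is one timed CRF field, a before/after mark, a listing and one more ARMS per sensor. The second ARMS may be slightly less favourable, because some restored pairs may carry genuine reference error, and the report should say so.
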